### **10.3.6. PK Analysis**

Drug concentrations of ABI-H0731 or PBO and NrtI will be listed at end of study:

- ABI-H0731 on ABI-H0731+NrtI therapy stratified by collection time window and collection day.
- NrtI on ABI-H0731+NrtI therapy as compared with PBO+NrtI therapy stratified by collection time window and study day.

Application to a population PK model may be applied, details of which will be provided in the pharmacometrics analysis plan. Results from of the population PK work will be reported outside of the clinical study report (CSR).

### **10.3.7. Safety Analysis**

All safety endpoints will be summarized using data from the Safety set. Safety analyses will involve examination of the incidence, severity and type of TEAEs reported, changes from Baseline (the assessment prior to first dose) in laboratory test results and in vital signs to specified time points throughout the study, and concomitant medications use.

#### **10.3.7.1. TEAEs**

Treatment-emergent adverse events reported during the study will be coded using the Medical Dictionary for Regulatory Activities (MedDRA) dictionary. Incidence of TEAEs will be summarized by treatment group and the following:

- Preferred term
- System organ class and preferred term
- System organ class, preferred term, and severity

These summaries will be presented for the following subsets:

- All adverse events
- Serious adverse events
- Drug-related adverse events

For tables reporting adverse events by severity, if a subject has multiple occurrences of an adverse event with the same organ class and preferred term, the most severe event will be presented.

#### **10.3.7.2. Clinical Laboratory Evaluation**

Laboratory parameters will be summarized by treatment group at each visit. Each summary will include the values of the laboratory parameters and their change from Baseline. Shift tables from Baseline will be presented for laboratory values in the chemistry and hematology panels. Parameters will be classified according to the laboratory reference normal ranges. A listing will be provided for out of normal range as well as clinically significant abnormal laboratory values.

#### **10.3.7.3. Vital Signs**

Vital signs, including heart rate, blood pressure, temperature, height, and body weight will be summarized by treatment group and time point. For each assessment of vital signs, change and percent change in vital signs from Baseline will be summarized by treatment group.

### **10.4. Interim Analysis**

No formal interim analysis is planned.

### **10.5. Independent Data Monitoring Committee**

An independent Data Monitoring Committee is not planned for this study.

## **10.6. Handling of Missing Data**

For the analysis of primary efficacy endpoint, missing HBV DNA data will be imputed using a multiple imputation method appropriate to the pattern of missingness. Details of the considered patterns and associated sensitivity analyses will be described in the SAP.

## **10.7. Multiplicity Adjustment**

No formal inference is planned in this study. Hence no multiplicity adjustment is required.

## **11. RESPONSIBILITIES**

### **11.1. Investigator Responsibilities**

#### **11.1.1. Good Clinical Practice**

This study will be conducted in compliance with IRB/IEC and International Council for Harmonisation (ICH) Good Clinical Practice (GCP) Guidelines; Title 21 Part 56 of the US Code of Federal Regulations (CFR) relating to IRBs/IECs and GCP as described in the US FDA CFR (21 CFR § 50, 56, 312; applicable ICH guidelines regarding clinical safety data management (E2A, E2B(R3)); European Community directives 2001/20, 2001/83, 2003/94, and 2005/28 as enacted into local law, and with ICH guidelines regarding scientific integrity (E4, E8, E9, and E10). In addition, this study will adhere to all local regulatory requirements, and requirements for data protection.

#### **11.1.2. Institutional Review Board (IRB)/Independent Ethics Committee (IEC)**

Before initiating a clinical study, the Investigator/institution must have written and dated approval/favorable opinion from the IRB/IEC, as well as for study protocol amendment(s), written ICF, any ICF updates, subject recruitment procedures (eg, advertisements), and any written information to be provided to subjects and a statement from the IRB/IEC that complies with GCP requirements. The IRB/IEC approval must identify the protocol version as well as the documents reviewed.

#### **11.1.3. Informed Consent**

The Investigator will explain the benefits and risks of participation in the study to each subject or the subject's legally acceptable representative and obtain written informed consent. Written informed consent must be obtained prior to the subject entering the study and before initiation of any study-related procedure (including administration of investigational product).

The Sponsor or its designee will provide a sample ICF. The final, version dated, ICF must be agreed to by the Sponsor and the IRB/IEC and will contain all elements in the sample form, in language readily understood by the subject. Each subject's original ICF must be personally signed and dated by the subject or by the subject's legally acceptable representative, and by the person who conducted the informed consent discussion. The original, signed ICF will be retained by the Investigator. The Investigator will supply all enrolled subjects with a copy of their signed ICF.

The ICF may need to be revised during the study should important new information become available that may be relevant to the safety of the subject. In this instance approval should always be given by the IRB/IEC and existing subjects informed of the changes and reconsented. This is documented in the same way as previously described.

The Investigator should encourage subjects to inform their primary physicians about their participation in the clinical study.

#### **11.1.4. Confidentiality**

All information generated in this study is considered confidential and must not be disclosed to any person or entity not directly involved with the study unless prior written consent is gained from the Sponsor. However, authorized regulatory officials, IRB/IEC personnel, and the Sponsor and the Sponsor's authorized representatives are allowed full access to the records.

Identification of subjects and eCRFs shall be by subject number only. If required, the subject's full name may be made known to an authorized regulatory agency or other authorized official.

#### **11.1.5. Study Files and Retention of Records**

Records must be retained in accordance with the current ICH guidelines on GCP. All essential study documents including records of subjects, source documents, eCRFs, and investigational product inventory must be kept on file.

Essential documents should be retained until at least 2 years after the last approval of a marketing application in an ICH region and until there are no pending or contemplated marketing applications in an ICH region, or until at least 2 years have elapsed since the formal discontinuation of clinical development of the investigational products. However, essential documents may be retained for a longer period if required by the applicable regulatory requirements or by agreement with the Sponsor. The Sponsor is responsible for informing the Investigator when these documents need no longer be retained.

The Investigator will not dispose of any records relevant to this study without written permission from the Sponsor and will give the Sponsor the opportunity to collect such records. The Investigator shall take responsibility for maintaining adequate and accurate hard copy source documents of all observations and data generated during this study. Such documentation is subject to inspection by the Sponsor, its representatives, and regulatory authorities.

If an Investigator moves, withdraws from an investigation, or retires, responsibility for maintaining the records may be transferred to another person who will accept responsibility. Notice of transfer must be made to and agreed by the Sponsor.

#### **11.1.6. Audits and Inspections**

The Sponsor or their designee, the CRO, may conduct audits at the investigative sites including, but not limited to, drug supply, presence of required documents, the informed consent process, and comparison of eCRFs with source documents. All medical records (progress notes) must be available for audit. The Investigator agrees to participate with audits conducted at a convenient time in a reasonable manner.

Government regulatory authorities may also inspect the site during or after the study. The Investigator or designee should contact the Sponsor and/or the CRO, immediately if this occurs. The site must cooperate fully with regulatory authorities or other audits conducted at a convenient time in a reasonable manner.

The purpose of an audit is to assess whether ethical, regulatory, and quality requirements are fulfilled.

#### **11.1.7. Protocol Compliance**

It is the responsibility of the Investigator to ensure that the study is conducted at his/her respective site in accordance with this protocol. Protocol compliance assessments will be conducted during routine site monitoring visits and ongoing data review by the Sponsor and CRO.

## **11.2. Sponsor Responsibilities**

### **11.2.1. Protocol Amendments and Modifications**

Protocol modifications, except those intended to reduce immediate risk to study subjects, may be made only by the Sponsor. A protocol change intended to eliminate an apparent immediate hazard to subjects may be implemented immediately, provided the IRB/IEC is notified within 5 days.

Any permanent, significant change to the protocol must be handled as a protocol amendment. The written amendment must be submitted to the IRB/IEC and the Investigator must await approval before implementing the changes. The Sponsor will submit protocol amendments to the appropriate regulatory authorities for approval.

If, in the judgment of the IRB/IEC, the Investigator, and/or the Sponsor, the amendment to the protocol substantially changes the study design and/or increases the potential risk to the subject and/or has an impact on the subject's involvement as a study subject, the currently approved written ICF will require similar modification. In such cases, subjects will be required to sign the amended informed consent prior to continued participation in the study.

### **11.2.2. Data Management**

A set of data management documents will be created under the responsibility of the Sponsor, or designated CRO, to describe the processes being used to ensure data quality.

The data management plan and other associated documentations will specify data capture methods, who is authorized to enter data, decisions about ownership of data, source data storage, which data will be transferred (including timing of transfers), and the origin/destination of data.

### **11.2.3. Study Report and Publications**

The Sponsor or its designee is responsible for preparing and providing the appropriate regulatory authorities with CSRs according to the applicable regulatory requirements. CSRs will be developed in accordance with the ICH E3 Guideline on the 'Structure and Content of Clinical Study Reports'. Local country requirements will be considered during CSR preparation.

The results of this study may be published or presented at scientific meetings. If this is foreseen, the Investigator agrees to submit all proposed manuscripts or abstracts to the Sponsor before submission. This allows the Sponsor to protect proprietary information and to provide comments. The Sponsor will comply with the requirements for publication of study results. In accordance with standard editorial and ethical practice, the Sponsor will generally support publication of multicenter studies only in their entirety and not as individual site data. In this case, a coordinating Investigator will be designated by mutual agreement.

Assembly Biosciences follows the guidelines and recommendations of the International Committee of Medical Journal Editors (ICMJE) and the International Society for Medical Publication Professionals when preparing publications associated with clinical studies ([ICMJE 2018](#), [Battisti 2015](#)).

## **13. APPENDICES**

Protocol Amendment 1 ABI-H0731-205  
08 September 2020

## APPENDIX 1 SCHEDULE OF ASSESSMENTS TABLE

Period or Visit	Screening		On Treatment									Follow-up		Premature Termination 	Unscheduled Visit 
	Day -45 to Day -1		Day 1	Wk 2	Wk 4	Wk 8	Wk 12	Wk 16	Wks 20-44 	Wk 48	Wks 52-96 	4-20 Wks Post 	24 Wks Post		
Study Day or Week	Visit 1	Visit 2													
Visit Window (days)			0	±3	±3	±3	±3	±3	±3	-3	±5	±5	±5	NA	NA
Informed Consent(s) 	X														
Demographics, medical history, and HBV history	X		X												
Liver staging 	X														
Height and weight 	X		X						X	X 		X			
Vital signs	X		X	X	X	X	X	X	X	X	X	X	X	X	X
Complete physical examination 	X		X						X	X 		X		X	
Symptom-directed physical				X	X	X	X	X	X	X 	X				X
12-lead ECG 	X		X				X		X 	X	X 		X	X	
Concomitant medications and AEs 	X		X	X	X	X	X	X	X	X	X	X	X	X	X
Confirm subject eligibility			X												
Complete randomization (IRT)			X												
Chemistry	X		X	X	X	X	X	X	X	X	X	X	X	X	X
Hematology	X		X	X	X	X	X	X	X	X	X	X	X	X	X
Coagulation	X		X		X	X	X	X	X	X	X	X	X	X	X
HbA1c	X														
Serum AFP	X														
FSH (females only)	X														
Pregnancy Test 	X		X	X	X	X	X	X	X	X	X	X		X	X
Urinalysis	X		X		X	X	X	X	X	X	X	X 	X	X	X
Urine drug test	X		X											X	X
HBV genotype			X												
HBV DNA	X	X 	X	X	X	X	X	X	X	X	X	X	X	X	X

## Protocol Amendment 1 ABI-H0731-205

08 September 2020

Period or Visit	Screening		On Treatment									Follow-up		Premature Termination 	Unscheduled Visit 
	Day -45 to Day -1		Day 1	Wk 2	Wk 4	Wk 8	Wk 12	Wk 16	Wks 20-44 	Wk 48	Wks 52-96 	4-20 Wks Post 	24 Wks Post		
Study Day or Week	Visit 1	Visit 2													
Visit Window (days)			0	±3	±3	±3	±3	±3	±3	-3	±5	±5	±5	NA	NA
HBV pgRNA	X		X	X	X	X	X	X	X	X	X	X	X	X	X
HBsAg, HBeAg 	X		X		X	X	X	X	X	X	X	X	X	X	X
HBcrAg			X		X	X	X	X	X	X	X	X	X	X	X
HBsAb, HBeAb	X		X				X		X 	X	X 		X	X	
Sample for HBV DNA sequencing and HBV nucleic acids	X		X	X	X	X	X	X	X	X	X	X	X	X	X
HIV Ab, HCV Ab, HDV Ab, HAV (IgM), HEV (IgM)	X														
Dosing diary			X	X	X	X	X	X	X	X	X	X	X		
IMP (ABI-H0731/PBO) accountability				X	X	X	X	X	X	X	X	X 		X	
IMP (ABI-H0731/PBO) dispensation			X	X	X	X	X	X	X	X	X	X 			
In-clinic IMP (ABI-H0731/PBO) dosing			X	X	X	X	X	X	X	X	X	X			
In-clinic NrtI dosing			X	X	X	X	X	X	X	X	X	X 			
PK Sample Collections 	ABI-H0731		X	X	X	X	X	X	X	X	X	X 		X	X
	NrtI		X	X	X	X	X	X	X	X	X	X 		X	X
Immunology (PBMC followed by serum cytokine sample collection) 	X		X	X	X		X		X 	X	X 	X 	X	X	
PaxGene® DNA and PaxGene® RNA samples 			X								X 		X 	X	
Optional pharmacogenomic sample collection			X												

Abbreviations: Ab=antibody; AE=adverse event; AFP=alpha fetoprotein; ALT=alanine aminotransferase; AST=aspartate aminotransferase; ECG=electrocardiogram; FSH=follicle-stimulating hormone; HAV=hepatitis A virus; HBcrAg=hepatitis B core-related antigen; HBeAb=HBeAg antibody; HBeAg=hepatitis B “e” antigen; HBsAb=HBsAg antibody; HBsAg=hepatitis B surface antigen; HBV=hepatitis B virus; HCV=hepatitis C virus; HDV=hepatitis D virus; HEV=hepatitis E virus; HIV=human immunodeficiency virus; IgM=immunoglobulin M; INR=international normalized ratio; IRT=Interactive Response Technology; NA=not applicable; PBO=placebo; PBMC=peripheral blood mononuclear cell; PK=pharmacokinetic; pgRNA= pre-genomic RNA; ULN=upper limit of normal; Wk=week; Wks=weeks.

-  Study visits occur every 4 weeks between Weeks 20 and 96 on treatment and between Weeks 4 and 20 Post Treatment.
-  Subjects who discontinue treatment before Week 48 should immediately undergo the assessments listed for the Premature Termination visit and then continue the scheduled follow-up assessments.
-  Any subjects with alanine aminotransferase (ALT) elevation (defined as  $ALT \geq 2 \times$  Baseline and  $\geq 10 \times$  ULN) should return to the clinic for an Unscheduled Visit to confirm the findings within 3 days of receipt of the original results. At the Unscheduled Visit, subjects should undergo the assessments described in [Section 7.7](#). If the ALT elevation is confirmed, the subject will return for an additional Unscheduled Visit at which the following tests: HBV DNA, HBV serologies (quantitative HBeAg [reflex qualitative HBeAg if quantitative HBeAg is negative] and HBsAg [reflex qualitative HBsAg if quantitative HBsAg is negative]), HAV IgM, HCV RNA, HDV RNA, and HEV IgM, will be performed. If the ALT is rising, the subject will return for additional Unscheduled Visits every 2-5 days until the ALT has stabilized. At these visits the following tests will be performed: HBV DNA, HBV serologies (quantitative HBeAg [reflex qualitative HBeAg if quantitative HBeAg is negative] and HBsAg [reflex qualitative HBsAg if quantitative HBsAg is negative]).
-  In addition to the study specific Informed Consent Form, a separate consent is required for the subject to provide an optional pharmacogenomic sampling.
-  Liver staging is to be performed to determine lack of cirrhosis or advanced liver disease as required by inclusion criteria and should be performed in a fasted state by FibroScan or other Sponsor-approved hepatic imaging method within 3 months of Screening.
-  Height is measured at the Screening visit only.
-  For the complete physical examination, assessment of the breasts and genitalia are not required unless indicated.
-  Complete physical exam and weight measurement are performed only at Weeks 48 and 96 visits, and at 24 Week post-treatment visit (if applicable).
-  A Symptom-directed physical exam is performed only at the visits when a complete physical exam is not performed.
-  During the study, any clinically significant ECG result or change from Baseline (Day 1) should be confirmed, and if confirmed, should be recorded as an AE. 12-lead ECG to be also performed at Weeks 24, 36, 48, and 96.
-  A serum pregnancy test for females of child-bearing potential is required at Screening. On Day 1 both urine and serum should be performed (subjects may begin treatment based on urine results; any subjects negative by urine subsequently found to be positive on serum should immediately discontinue treatment and may be replaced). All post-Day 1 pregnancy tests may be conducted by urine dipstick. If positive on dipstick, reflex to serum.
-  Urinalysis will be conducted 4 and 24-Weeks Post Treatment
-  A second, confirmatory HBV DNA should be drawn 10 to 14 days after the initial Screening visit during the Screening assessment period. If the results from these 2 samples indicate a decline in HBV DNA then a third sample will be collected to ensure virologic plateau prior to randomization.
-  If quantitative HBsAg or HBeAg are negative at any visit subsequent to Screening, reflex to qualitative.
-  HBsAb and HBeAb tests are performed at Weeks 24, 48, 72, and 96.
-  Final study drug dispensation is performed at Week 92, and final study drug accountability is performed at Week 96. NrtI will be continued throughout the 24-week follow-up period.
-  If the subject inadvertently administers study drug prior to collection, a PK sample should still be drawn. Refer to [Section 10.3.6](#).
-  Predose PK samples for ABI-H0731 or PBO and NrtI on Day 1 and Weeks 4 and 48. Postdose PK samples for ABI-H0731 and NrtI may be collected from 2 to 4 hours postdose on Day 1, and between 30 min and 2 hours after in-clinic study drug + NrtI administration at Weeks 2, 8, 12, 24, and 28. Postdose samples on Weeks 16 and 20 may be collected between 4 and 6 hours after in-clinic study drug + NrtI administration.
-  Collect a PK sample with other central labs at week 4 Post-treatment follow-up visit.
-  Immunology (PBMCs and serum cytokine sample) collections occur every 12 weeks at Weeks 24, 36, 48, 60, 72, 84, and 96 visits, at selected sites only. At follow-up, collect at 4 Weeks Post-treatment, 12 Weeks Post-treatment, and 24 Weeks Post-treatment visits, and at the premature termination visit.
-  PaxGene® RNA only at Week 96, 24-Weeks post treatment visit, and on premature termination visit.
-  Concomitant medications must be recorded in the subjects' source documentation until the end of study (completion of follow-up period); NrtIs should be followed through to the end of the follow-up period.
-  In-clinic NrtI administration only required at 4 weeks post visit.

Protocol Amendment 1 ABI-H0731-205

08 September 2020

---

 Only the subjects that provide PBMCs at Screening at selected sites will undergo additional PBMCs, serum cytokine, PaxGene® DNA and PaxGene® RNA sample collection at the specified timepoints. Note that PaxGene® DNA sample will only be collected on Day 1.

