## 7.7. **Unscheduled Visit**

An unscheduled visit may be performed at any time at the discretion of Investigator in order to further evaluate a subject. The specific assessments to be performed at these visits would be determined by the Investigator according to nature of the subject specific follow-up required, however at a minimum the assessments would include the following:

- Vital signs (temperature, heart rate, respiration rate and blood pressure)
- Symptom-directed physical examination
- Review concomitant medications
- Review AEs
- Laboratory analyses (additional details are provided in the Laboratory Manual):

- Safety labs: chemistry, hematology, coagulation, urinalysis, urine drug test, urine pregnancy test for females of child-bearing potential only (see [Appendix 2](#))
- Virology: HBV DNA, HBV pgRNA, HBsAg, HBeAg, HBcrAg, sample for HBV sequencing, and HBV nucleic acids (see [Appendix 2](#))
- PK samples: samples for ABI-H0731 or PBO and NrtI. See [Section 7.10](#) for additional information on PK sampling.

Assessments performed should be documented in the subject's source documentation. Clinical laboratory assessments should be conducted through the central laboratory.

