### **7.9.1. Discontinuation from Treatment**

If an individual subject is, in the judgement of the Investigator, not satisfactorily tolerating study drug treatment due to AEs, then in consultation with the Sponsor, the subject may discontinue treatment with ABI-H0731 or PBO. NrtI may be continued at the discretion of the Investigator. Discontinuation from treatment does not mean discontinuation from the study. Subjects who prematurely discontinue treatment should immediately undergo the assessments listed for the Premature Termination visit ([Section 7.8](#)) and then continue scheduled follow-up assessments ([Section 7.6](#)).

In this study, subjects will be closely monitored for ALT elevations and declining hepatic function. Procedures to be followed for these subjects are described in [Section 9.4](#). Study treatment will be discontinued in subjects with confirmed evidence of declining hepatic function during treatment, a Premature Termination visit ([Section 7.8](#)) will be completed, and subjects will subsequently undergo the follow-up assessments described in [Section 7.6](#).

Any subjects negative by urine pregnancy test at Baseline (Day 1) who are subsequently found to be positive on serum pregnancy test should immediately discontinue treatment with ABI-H0731 or PBO. NrtI may be continued if indicated based on Investigator judgment in accordance with local practice and the approved NrtI package insert. These subjects may be replaced at the discretion of the Sponsor.

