#### **8.5. Abnormal Laboratory Test Values**

In the event of abnormal laboratory test values, the tests should be repeated immediately. If the Investigator considers the abnormality to be clinically significant, it should be reported as an AE and followed up until it returns to the normal range and/or an adequate explanation of the abnormality is found.

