### **9.4. Management of On-treatment and Post-treatment ALT Elevations**

All subjects participating in the study will be closely monitored for ALT elevations and/or signs of potential decline in hepatic function. Subjects experiencing ALT elevations  $\geq 2 \times$  Baseline or on-treatment nadir and  $> 2 \times$  ULN during study treatment or during post-treatment follow-up should be closely monitored with regular unscheduled visits every 1 to 2 weeks at the discretion of the Investigator. For these subjects, at each timepoint, an Unscheduled Visit should be conducted with completion of assessments as described in [Section 7.7](#). Additionally, the following guidance is provided for management of subjects with ALT elevations:

- All subjects with an ALT elevation on treatment, defined as ALT  $> 2 \times$  Baseline or on-treatment nadir and  $\geq 10 \times$  ULN, should have the ALT findings confirmed within 3 days of receipt of the original results. To confirm the ALT finding, the subject should return to the clinic for an Unscheduled Visit and undergo all assessments as noted in [Section 7.7](#) (Unscheduled Visit).
- If the ALT elevation is confirmed, then an additional Unscheduled Visit will be performed to further evaluate the subject. At this visit, the following laboratory tests will be performed: ALT, AST, total bilirubin (if total bilirubin is elevated, reflex to Direct Bilirubin), serum albumin, HBV DNA, and quantitative HBV serologies (HBeAg [reflex qualitative HBeAg if quantitative HBeAg is negative] and HBsAg [reflex qualitative HBsAg if quantitative HBsAg is negative]), HAV IgM, HCV RNA, HDV RNA, and HEV IgM.
  - If an intercurrent illness is determined to be causal, subjects with an ALT elevation without declining hepatic function and without contraindications may continue

treatment and the intercurrent illness should be treated as deemed medically appropriate by the Investigator.

- Subjects with an ALT elevation without declining hepatic function and without contraindications may continue treatment with study drug under close observation.

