- If ALT is rising at the confirmatory visit, subjects should return for an **Unscheduled Visit** every 2 to 5 days until the ALT elevation has stabilized. At these visits the following laboratory tests will be performed: ALT, AST, total bilirubin (if total bilirubin is elevated, reflex to Direct Bilirubin), serum albumin, INR, HBV DNA, and quantitative HBV serologies (HBeAg [reflex qualitative HBeAg if quantitative HBeAg is negative] and HBsAg [reflex qualitative HBsAg if quantitative HBsAg is negative]). Subjects whose ALT has stabilized should continue to be monitored weekly (or more frequently, as deemed necessary by the treating physician) until ALT values return to normal or Baseline levels.
  - Subjects with an ALT elevation without declining hepatic function and without contraindications should discontinue study drug if the ALT remains persistently elevated for >4 weeks
- Subjects with confirmed ALT elevation with evidence of declining hepatic function should be discontinued from study treatment. This is defined as:
  - ALT elevation  $\geq 2 \times$  Baseline or nadir and  $> 2 \times$  ULN AND
    - Direct bilirubin increase to  $\geq 2 \times$  Baseline and  $\geq 2 \times$  ULN OR
    - Albumin decline  $\geq 0.5$  g/dL OR INR  $> 2 \times$  Baseline OR
    - Symptoms of liver inflammation (eg, fatigue, weakness, lack of appetite, nausea, vomiting, jaundice, or discolored feces)
- Subjects with evidence of declining hepatic function should return for an **Unscheduled Visit** every 2 to 5 days until the relevant laboratory values stabilize. Subjects whose hepatic function has stabilized should continue to be monitored weekly (or more frequently as deemed necessary by the Investigator) until the relevant laboratory values return to normal or Baseline.
- **Post-treatment ALT Elevation**

Following cessation of study drug treatment under this protocol all subjects will be closely followed for ALT elevations and/or signs of potential decline in hepatic function. This applies to all subjects whether they prematurely discontinue study drug or complete the study per protocol. Any subject with a post-treatment ALT elevation without evidence of declining hepatic function or a post-treatment ALT elevation with evidence of declining hepatic function as defined above, will be evaluated as noted above.

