Urinary				
Parameter	Grade 1 Mild	Grade 2 Moderate	Grade 3 Severe	Grade 4 Potentially Life-threatening
Urinary Tract Obstruction	NA	Signs or symptoms of urinary tract obstruction without hydronephrosis or renal dysfunction	Signs or symptoms of urinary tract obstruction with hydronephrosis or renal dysfunction	Obstruction causing life-threatening consequences

Abbreviations: NA=not applicable.

Protocol Amendment 1 ABI-H0731-205

08 September 2020

Laboratory Valuesk: Chemistries*				
Parameter	Grade 1 Mild	Grade 2 Moderate	Grade 3 Severe	Grade 4 Potentially Life-threatening
Acidosis	NA	pH $\geq$ 7.3 to <LLN	pH<7.3 without life- threatening consequences	pH<7.3 with life- threatening consequences
Albumin, Low (g/dL; g/L)	3.0 to <LLN 30 to <LLN	$\geq$ 2.0 to <3.0 $\geq$ 20 to <30	<2.0 <20	NA
Alkaline Phosphatase, High	1.25 to <2.5 x ULN	2.5 to <5.0 x ULN	5.0 to <10.0 x ULN	$\geq$ 10.0 x ULN
Alkalosis	NA	pH >ULN to $\leq$ 7.5	pH >7.5 without life- threatening consequences	pH >7.5 with life- threatening consequences
ALT or SGPT, High Report only one	1.25 to <2.5 x ULN	2.5 to <5.0 x ULN	5.0 to <10.0 x ULN	$\geq$ 10.0 x ULN
Amylase (Pancreatic) or Amylase (Total), High Report only one	1.1 to <1.5×ULN	1.5 to <3.0×ULN	3.0 to <5.0×ULN	$\geq$ 5.0×ULN
AST or SGOT, High Report only one	1.25 to <2.5 x ULN	2.5 to <5.0 x ULN	5.0 to <10.0 x ULN	$\geq$ 10.0 x ULN
Bicarbonate, Low (mEq/L; mmol/L)	16.0 to <LLN 16.0 to <LLN	11.0 to <16.0 11.0 to <16.0	8.0 to <11.0 8.0 to <11.0	<8.0 <8.0
Bilirubin Direct Bilirubin, High	NA	NA	>ULN with other signs and symptoms of hepatotoxicity.	>ULN with life- threatening consequences (eg, signs and symptoms of liver failure)
Total Bilirubin, High	1.1 to <1.6×ULN	1.6 to <2.6×ULN	2.6 to <5.0×ULN	$\geq$ 5.0×ULN
Calcium, High (mg/dL; mmol/L)	10.6 to <11.5 2.65 to <2.88	11.5 to <12.5 2.88 to <3.13	12.5 to <13.5 3.13 to <3.38	$\geq$ 13.5 $\geq$ 3.38
Calcium (Ionized), High (mg/dL; mmol/L)	>ULN to <6.0 >ULN to <1.5	6.0 to <6.4 1.5 to <1.6	6.4 to <7.2 1.6 to <1.8	$\geq$ 7.2 $\geq$ 1.8
Calcium, Low (mg/dL; mmol/L)	7.8 to <8.4 1.95 to <2.10	7.0 to <7.8 1.75 to <1.95	6.1 to <7.0 1.53 to <1.75	<6.1 <1.53

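### Appendix 1 footnote 3 omits the on-treatment nadir from the ALT trigger that Section 9.4 uses for the 3-day confirmation and viral hepatitis work-up

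*Combined protocol and SAP*

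**What the plan says.** Section 9.4 sets the rule for a marked on-treatment ALT rise. Subjects whose ALT is more than 2× Baseline or on-treatment nadir, and at least 10×ULN, "should have the ALT findings confirmed within 3 days of receipt of the original results". If the rise is confirmed, a further unscheduled visit adds HAV IgM, HCV RNA, HDV RNA and HEV IgM to the liver and HBV tests. If ALT is still rising, visits follow every 2 to 5 days. Section 7.9.1 names Section 9.4 as the governing text for subjects with ALT elevations: "Procedures to be followed for these subjects are described in" that section.

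Footnote 3 of the Appendix 1 schedule of assessments gives the same 3-day deadline, the same four non-HBV hepatitis tests and the same 2-to-5-day visits. It says subjects "should return to the clinic for an Unscheduled Visit to confirm the findings within 3 days of receipt of the original results". Its definition of the elevation is ALT at least 2× Baseline and at least 10×ULN. The nadir appears nowhere in the footnote, which cites Section 7.7 but not Section 9.4.

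Both texts belong to Protocol Amendment 1 and are current.

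**The concern.** Baseline is fixed before the first dose (Section 10.3.7), so it cannot stand in for a nadir reached later. A subject who enters with a high ALT, improves on treatment and then flares may be far above the nadir yet below twice Baseline. The protocol expects ALT to fall in some subjects: normalization of an abnormal Baseline ALT is a secondary endpoint.

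Footnote 3 reads as a complete instruction, with definition, deadline, tests and repeat-visit rule, and it sits in the table that sites use to plan visits. A site relying on it alone would not be required, for such a rebound, to confirm within 3 days, run the HAV, HCV, HDV and HEV tests, or see the subject every 2 to 5 days while ALT rises. Every value in question is at least 10×ULN, which the row "ALT or SGPT, High" in Appendix 3 grades as 4.

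The omission looks like a drafting slip. Section 9.4 uses Baseline or nadir in all three of its ALT definitions: the lower monitoring tier, the confirmation trigger and the stop for declining hepatic function. Appendix 6 lists footnote 3 among those revised in Amendment 1 and gives alignment with Section 9.4 as a reason.

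**Working it through.** **Inputs**

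- Section 9.4 trigger: ALT >2× Baseline or on-treatment nadir, and ≥10×ULN.
- Appendix 1 footnote 3 trigger: ALT ≥2× Baseline, and ≥10×ULN.
- Section 5.3, exclusion criterion 13: ALT >10×ULN is excluded, so Baseline can be as high as 10×ULN.
- Appendix 3: ALT ≥10×ULN is Grade 4.

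**Set-up.** Let b = Baseline, n = on-treatment nadir and x = current ALT, all in multiples of ULN. Read Section 9.4 as met if either reference value is exceeded.

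- Section 9.4: x ≥ 10 and (x > 2b or x > 2n)
- Footnote 3: x ≥ 10 and x ≥ 2b

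**Where only Section 9.4 triggers.** This needs x ≥ 10, x > 2n and x < 2b together.

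- x ≥ 10 with x < 2b requires b > 5. For b ≤ 5, any x ≥ 10 is already at least 2b, so leaving out the nadir changes nothing.
- x > 2n with x < 2b requires n < b. If ALT never falls below Baseline, there is no such gap.

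For a nadir below 5×ULN, 2n is below 10, so the 10×ULN floor sets the lower end and 2b sets the upper end:

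| Baseline (×ULN) | Upper end, 2b | ALT flagged by Section 9.4 only (×ULN) |
|---|---|---|
| 5 | 10 | none |
| 6 | 12 | 10 to <12 |
| 7 | 14 | 10 to <14 |
| 8 | 16 | 10 to <16 |
| 9 | 18 | 10 to <18 |
| 10 | 20 | 10 to <20 |

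At a nadir of exactly 5×, x = 10 is not above 2n, so the lower end becomes >10. For a nadir above 5× but below Baseline, the gap runs from >2n to <2b. With b = 10 and n = 8, that is >16 to <20×ULN.

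**Example (assumed values).** b = 8, n = 1, x = 12.

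- Section 9.4: 12 ≥ 10, and 12 > 2×1 = 2, so it triggers.
- Footnote 3: 12 ≥ 10, but 12 < 2×8 = 16, so it does not. The current value is 12/8 = 1.5× Baseline and 12/1 = 12× nadir.

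**Where only footnote 3 triggers.** This happens only at exact equality, x = 2b, when ALT has not fallen below Baseline and b ≥ 5. At b = 6 with no fall and x = 12, footnote 3 accepts ≥ while Section 9.4 wants >. This is trivial.

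**The case against.** The strongest reply is that Section 9.4 already contains the right rule and applies it to all subjects on treatment. Section 7.9.1 points there, and footnote 3 does not claim to limit it. A site that follows the whole protocol has no gap. That stands, and it keeps the point minor. It does not make the footnote correct, since a reader of the schedule meets a different threshold with no reference to the governing section.

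Second, other safeguards catch these subjects. Section 8.5 states: "In the event of abnormal laboratory test values, the tests should be repeated immediately". Under the lower tier in Section 9.4 (at least 2× Baseline or nadir and >2×ULN), subjects "should be closely monitored with regular unscheduled visits every 1 to 2 weeks at the discretion of the Investigator". The stopping rule also counts a rise from nadir: "Subjects with confirmed ALT elevation with evidence of declining hepatic function should be discontinued from study treatment". These are real, but two of the three sit in Section 9.4 itself, so they do not help a site that looks only at the schedule. None of them mandates the non-HBV hepatitis tests. The Section 7.7 minimum is "Virology: HBV DNA, HBV pgRNA, HBsAg, HBeAg, HBcrAg, sample for HBV sequencing, and HBV nucleic acids", with no HAV, HCV, HDV or HEV test. Section 7.7 lets the Investigator add tests, and Section 8.5 expects a clinically significant abnormality to be followed until it normalizes or is explained. Omission is therefore less likely than the bare minimum suggests, but the tests remain optional.

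Third, the reach is very small. It takes a Baseline ALT above 5×ULN after more than 12 months on a stable NrtI (inclusion criterion 7), then a fall, then a rebound that stays below twice Baseline. The protocol also reports no Grade 4 laboratory abnormality among the 92 subjects in Study 211 through Week 24. All of this stands.

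Fourth, the footnote's test lists omit the liver tests that Section 9.4 names. That is a separate mismatch, largely covered by the chemistry panel in Section 7.7 and the elevated-ALT panel in Table 8.

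**Conclusion.** The concern holds and is minor. Footnote 3 states the wrong trigger against the protocol's own Section 9.4. For Baseline ALT above 5× and up to 10×ULN with a nadir below 5×, the two disagree from 10×ULN up to just under twice Baseline; at Baseline 10× the gap is 10 to <20×ULN. For Baseline at or below 5×ULN, or when ALT never falls below Baseline, they agree except at exact equality.

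This rests on reading Section 9.4 as satisfied by either reference value. How many subjects would fall in the gap cannot be estimated, because the documents give no ALT distribution for this population. The study stopped with 2 subjects randomized (SAP Section 1) and the analysis is by-subject listings only (SAP Section 3), so no result is affected. No harm to any subject is claimed.

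**What to change.** In Appendix 1 footnote 3, replace the definition with the Section 9.4 trigger: ALT >2× Baseline or on-treatment nadir and ≥10×ULN (see Section 9.4). Citing Section 9.4 for the definition, without restating it, works equally well and leaves a single text to maintain. Using the Section 9.4 wording also removes the > versus ≥ difference.

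The cost is one line in a protocol amendment. It adds no visit or test beyond what Section 9.4 already requires. Since this trial has ended, the practical use is in any later protocol that reuses the schedule.
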